CPET: VO₂ peak, peak power, test duration of entire test, time to AT, work efficiency (VO₂ work rate slope), and ventilator equivalent (VE/VO₂) will be obtained.

EIM: An EIM will be used to measure skeletal muscle health. Resistance, reactance and phase of multiple muscles will be measured.

6MWT: Meters walked in 6 minutes will be recorded (to the nearest meter). Distance in meters will be recorded at each minute interval. Speed will be calculated.

Timed tests: Participants will be timed in the performance of the following: 10 meter walk test, supine to stand, ascend 4 stairs, descend 4 stairs. They will be graded on an ordinal scale.

Myotools: Force required for participants to squeeze the grip dynamometer and pinch the pinch gauge. The best effort of 3 trials will be recorded for grip and pinch strength.

Biodex: Biodex will be used to test muscle groups using a dynamic sub-max fatigue test with a repetitive motion. Blood pressure will be taken prior to testing to confirm the patient is not hypertensive (>140/90). Outcome measures will include peak torque measured in newton meters and number of repetitions to 50% decline in peak torque.

Arterial Occlusion Muscle Oxygenation Capacity Test: The tissue saturation index will be calculated as $TOI = [O_2-Hb] / Tot-Hb$. The rate of decline and rise in TOI will be the main muscle tissue saturation measures.

MFM: The final outcome is a percentage based score of each domain and the total score.

PROMIS, FACIT, MFI, NeuroQoL: Questionnaires will be scored based on each scale's requirements.

MRI: The outcomes will be muscle mass via T1, fat composition via T1 to T2 comparison, water composition via T1 to T2 comparison and chemical composition (lipids) via MRS.

Saliva collection: FBI, melatonin, cortisol and DHEA levels will be obtained.

Qualitative interview: Responses to the interview will be obtained and major themes will be identified.

10. Statistical Analysis

a. Analysis of data/ study outcomes

Natural history study (Phase 1 of protocol):

During the natural history phase of the study, we will take one look at the data prior to the final analysis with the following two approaches:

- 1) After 30 participants complete their baseline visit, we will compare their baseline outcome measure values against healthy controls. For the primary outcomes, 15-F2t-isoprostane and 6MWT distance will be compared against healthy individuals. This analysis will be repeated when all baseline visits are completed.

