Hypothesis: 15-F2t-isoprostane will be significantly increased in RYR1-RM myopathy patients compared to healthy individuals.

Hypothesis: 6MWT distance will be significantly decreased in RYR1-RM patients compared to healthy individuals.

- 2) After 30 participants complete their 2nd visit at 6 months (prior to starting study drug/placebo), disease progression will be assessed using paired t-tests to determine changes between 0 and 6 month visits for each outcome measure. For the primary outcome measures, 15-F2t-isoprostane and 6MWT will be assessed for change between 0 and 6 months. This analysis will be repeated when all 6 month visits are completed.

Hypothesis: 15-F2t-isoprostane concentration will not change significantly between 0 and 6 months in RYR1-RM myopathy patients.

Hypothesis: 6MWT distance will not change significantly between 0 and 6 months in RYR1-RM patients.

The purpose of the above interim look analyses (under #1) is to confirm that the affected subjects are different from healthy individuals. Because of the rolling nature of the study and the length of time involved to complete the first phase of the study, this allows evaluate whether these outcomes are different from healthy individuals, as expected, in order to confidently proceed with the study. The purpose of the above interim look analysis (under #2) is to characterize the natural history and variability of the RYR1-RM patients for these specific outcome measures and to contribute novel data to the field of RYR1 as soon as possible for future trial design, given that an N of 30 is a large number in rare disease.

Optimal measures for fatigability in RYR1-RM will be determined using paired t-tests for 6MWT distance and speed, time for graded functional tests, and fatigue index for biodex fatigue test. Correlative analysis (Pearson correlation and/or Spearman rho) will be used to examine the linear relationship between subjective fatigue measures (FACIT and MFI) and the salivary fatigue biomarker to the objective fatigability measures mentioned above as well as to compare forced vital capacity to slow vital capacity. Spearman rho correlation, Pearson correlation and or Bland Altman analysis will also be used to examine the relationship between slow vital capacity and forced vital capacity.

Reliability will be assessed for PROMIS, FACIT, MFI, MFM, and NeuroQoL by Cronbach's alpha for internal consistency and by Intraclass correlation coefficient for test-retest. If the test-

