Date: July 2, 2018

RE: Statistical Analysis Plan for Protocol 15-NR-0072 Antioxidant therapy in RYR1-related congenital myopathy

Primary outcome measures

Where to find data (variables) for the below analyses in locked excel files:

- 1) AE_Spreadsheet_Demographics_LOCKED_2018.3.29
- 2) Urinelsoprostane_6MWT_LOCKED_2018.3.29
- 3) PillCount_PlasmaRedox_SalivaFBI_SMOxidativeStressDCFH_LOCKED_2018.3.29

Descriptive statistics

- Assess data distribution (i.e. basic descriptive statistics) for demographics (sex, ethnicity, smoking_status, alcohol_consumption, age_month0, height_month0, weight_month0, bmi_month0)

- Assess data distribution for urine isoprostane (all variables)

- Assess data distribution for six-minute walk test (predicted_distance_walked_month0, min_6_distance_month0, predicted_distance_walked_month6, min_6_distance_month6, predicted_distance_walked_month12, min_6_distance_month12).

- Assess data distribution for skeletal muscle oxidative stress (all variables),

- If possible, also assess data distribution for plasma redox (GSH_GSSG_month0, GSH_GSSG_month6, GSH_GSSG_month12, CYS_CYSS_month0, CYS_CYSS_month6, CYS_CYSS_month12).

- Assess data distribution for pill count (percent_compliance_month12).

- Descriptive statistics (frequency, mean, median, SD, SEM, IQR, range) for all the above for entire cohort at baseline (month 0) for demographics.
- Repeat abovementioned descriptive statistics split by treatment group (NAC and placebo) at baseline.
- Assess the frequency of AEs by system organ class (System Organ Class (SOC) (AE only) and by Preferred Term (Preferred Term (AE only)).

Natural history phase analyses

During the natural history phase of the study (month 0 to month 6), we will take one look at the data prior to the final analysis with the following two approaches:

1. After 30 participants complete their baseline visit, we will compare their baseline outcome measure values against healthy controls. The mean values for the primary outcome measures (corrected 15-F2t-isoprostane concentration and 6MWT distance) will be compared against existing data for otherwise healthy individuals using summary independent t-tests and/or standardized mean difference (i.e. Hedge's g which is a measure of effect size between two means, weighted by n). This analysis will be repeated when all baseline visits are completed.

Null Hypothesis (H_0)

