There will be no difference in mean corrected 15-F2t-isoprostane concentration or 6MWT distance, between the *RYR1*-RM and otherwise healthy individuals.

Alternative Hypothesis (H_1)

Corrected 15-F2t-isoprostane concentration will be significantly increased and 6MWT total distance will be significantly decreased in *RYR1*-RM myopathy patients when compared to otherwise healthy individuals.

2. After 30 participants complete their 2nd visit at 6 months (prior to starting study drug/placebo), disease progression will be assessed using paired t-tests to determine changes between 0 and 6-month visits for each outcome measure. For the primary outcome measures (corrected 15-F2t-isoprostane concentration and 6MWT) change between 0 and 6-month time points will be assessed. This analysis will be repeated when all 6-month visits are completed.

Null Hypothesis (H₀)

Corrected 15-F2t-isoprostane concentration and 6MWT total distance will not change significantly between 0 and 6 months in *RYR1*-RM myopathy patients.

Alternative Hypothesis (H₁)

There will be a statistically significant difference between 0 and 6-month values for corrected 15-F2t-isoprostane concentration and/or 6MWT total distance in *RYR1*-RM myopathy patients.

Intervention phase analyses (month 6 to month 12)

- Use an independent t-test (or non-parametric equivalent) to compare pre-intervention (month 6) values for demographics, urine isoprostane and six-minute walk test between NAC versus placebo groups.
- Using multiple imputation (x40 datasets and minimum/maximum value constraints from *per protocol* data) impute missing month 12 data.
- The following GLM should be run both *per protocol* and with ITT datasets.
 1. Run a general linear model comparing month 12 month corrected 15-F2t-isoprostane concentration (corrected_f2-isop_month12, corrected_f2-isop_PGF2alpha_ratio_month12) between NAC and placebo groups controlling for pre-intervention value. Run this model again controlling for established *a priori* confounders including age, sex, height, weight, BMI, smoking status, alcohol status. Variables that do not contribute significantly to the model may be removed. (Exclude RYR023, RYR024, and all healthy volunteers).

Null Hypothesis (H₀)

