There will be a statistically significant and/or clinically meaningful difference between 0 and 6-month graded functional tests (time to completion); Biodex (fatigue indices); Myotools values (grip and pinch strength), MFM (D1, D2, D3 and total % of maximum score), PROMIS (scale scores), FACIT (total score), NeuroQoL (scale scores), MRI (intramuscular fatty infiltration), MFI-20 (total score) in *RYR1*-RM myopathy patients.

3. Additionally, the following will be analyzed:

Optimal measures for fatigability in *RYR1*-RM will be determined using paired t-tests for 6MWT distance and speed, time for graded functional tests, and fatigue index for biodex fatigue test.

Spearman rho correlation, Pearson correlation and/or Bland Altman analysis will also be used to examine the relationship between slow vital capacity and forced vital capacity (L and % predicted). Descriptive statistics and change between baseline and 6 months will be assessed for FVC and SVC (L and % predicted).

Reliability will be assessed for PROMIS, FACIT, MFI, MFM, and NeuroQoL by Cronbach's alpha for internal consistency and by Intraclass correlation coefficient for test-retest.

Intervention phase analyses (intent-to-treat)

- Use an independent t-test (or non-parametric equivalent) to compare baseline values for all secondary outcomes above between NAC versus placebo groups. General linear modeling will be used to control for possible confounders such as such as but not limited to baseline values, gender, age, and baseline values. Log transformed values may be used if there is no bell curve. We will use an alpha of 0.05 to determine significance. Variables that do not contribute to the model may be removed.
- Using multiple imputation (x40 datasets and minimum/maximum value constraints from per protocol data) impute missing month 12 data.
- The following GLM should be run both *per protocol* and with ITT datasets.
- General linear model comparing month 12-month data between NAC and placebo groups (controlling for possible confounders such as but not limited to: baseline value, age, sex, height, weight, BMI, smoking status, alcohol status).

Exploratory Outcome Measures

Aim 1: Anaerobic threshold, NIRS; secreted ER calcium monitoring proteins (SERCAMP) assay in blood and muscle

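### The six-month 6MWT progression test uses raw metres pooled over children and adults, so growth in children is mixed with disease change; percent-predicted change and an age split should be added.

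*SAP*

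**What the plan says.** SAP, Natural history phase analyses, item 2: "disease progression will be assessed using paired t-tests to determine changes between 0 and 6-month visits for each outcome measure". The null hypothesis there is that "6MWT total distance will not change significantly between 0 and 6 months". Protocol section 10a has the same plan and states the trial's expectation that "6MWT distance will not change significantly between 0 and 6 months in RYR1-RM patients". Protocol section 9 gives the unit: "Meters walked in 6 minutes will be recorded (to the nearest meter".

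Patients are 7 years or older with no upper age limit (Protocol section 3b). Item 2 has no age stratum, size covariate or percent-predicted outcome.

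Elsewhere the plan does allow for body size or age:

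- The SAP's Descriptive statistics list predicted distance beside observed distance at every visit: "predicted_distance_walked_month0, min_6_distance_month0, predicted_distance_walked_month6, min_6_distance_month6, predicted_distance_walked_month12, min_6_distance_month12". The 6MWT data are in the locked file "Urinelsoprostane_6MWT_LOCKED_2018.3.29". Predicted distance enters no test or model.
- For lung volumes, the SAP's secondary natural-history analyses say that "change between baseline and 6 months will be assessed for FVC and SVC (L and % predicted"), so change is examined on both scales.
- The SAP's month-12 model for 6MWT names age, sex and height as a priori confounders.
- Protocol section 10a plans an adult-versus-child subgroup analysis, but only in the randomized phase and because of dosing.
- Protocol section 4d repeats height at visits 2 and 3 in children only.

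**The concern.** A paired change with no concurrent control contains everything that moves the measurement over six months. In a growing child, that is any disease change plus whatever distance growth adds. Averaged with adults, the pooled mean moves up by the share of children times their average gain from growth.

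This can act in two ways. A real decline relative to expected growth can be offset, which favours the no-change result that the protocol expects. If there is no decline, growth alone can produce a significant improvement.

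The natural-history result is meant to describe course and variability for future trial design (Protocol section 10a). Paired tests of 6MWT distance and speed are also to be used in choosing the best fatigability measures. The plan gives lung volumes a size-adjusted change analysis, but not its primary functional outcome.

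**Working it through.** **The plan's own figure.** No SD, effect size or power is stated for the Phase 1 6MWT test, so there is nothing to reproduce for it. The stated 38 per group (Protocol section 10b) concerns glutathione in the randomized phase. It reproduces (power 0.798 at 37 and 0.809 at 38) but does not bear on this point.

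**Inputs from the documents.** First look at n=30, repeated when all 6-month visits are complete (SAP item 2). Target completers 76 (Protocol section 3a). Alpha 0.05, taken as two-sided. The final Phase 1 n is not given, so 76 is a planning figure only.

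**Inputs assumed, not in the documents.** Share of children f = 0.30 to 0.50; gain from growth in six months g = 5 to 15 m; SD of change 30 to 50 m.

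**Formulas.** Shift of the pooled mean = f × g. SE = SD/√n. With no true progression, P(significant) = Φ(−1.96 − d) + 1 − Φ(1.96 − d), where d = shift/SE.

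| Case | f × g | SD | n | SE | d | P(significant) |
|---|---|---|---|---|---|---|
| Low | 0.30 × 5 = 1.5 m | 50 | 30 | 9.13 | 0.16 | 5.3% |
| Midpoint | 0.40 × 10 = 4.0 m | 40 | 30 | 7.30 | 0.55 | 8.5% |
| High | 0.50 × 15 = 7.5 m | 30 | 30 | 5.48 | 1.37 | 28% |
| Low | 1.5 m | 50 | 76 | 5.74 | 0.26 | 5.8% |
| Midpoint | 4.0 m | 40 | 76 | 4.59 | 0.87 | 14% |
| High | 7.5 m | 30 | 76 | 3.44 | 2.18 | 59% |

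An exact t calculation gives slightly lower values, for example 26% and 58% in the two high cases.

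**If patients gain only part of the predicted rise.** Suppose patients walk 70% of predicted and scale in proportion (assumed). The high-case shift becomes 0.7 × 7.5 = 5.25 m, so d is 0.96 at n=30 and 1.53 at n=76. P(significant) falls to 16% and 33%.

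**Masking.** Assume a true decline of 20 m relative to expected and an SD of 45 m, with a noncentral t calculation that adds the child/adult spread f(1−f)g² to the variance. Power to detect the decline is then:

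| n | No growth shift | Shift 3.5 m (0.35 × 10) | Shift 5 m (0.50 × 10) |
|---|---|---|---|
| 30 | 65% | 49% | 42% |
| 76 | 97% | 88% | 81% |

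**The case against.** **The size is assumed.** This stands. The 59% needs the extreme of all three inputs as well as n=76, a completer target set for the randomized phase. At the low end the effect is negligible.

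**Metres may be the right quantity.** The stated purpose is to describe these specific measures for future trials. A trial that uses distance as its endpoint needs the untreated drift in metres, growth included, and the paired test is unbiased for that. This also stands, and is why the metres test should stay. What it does not justify is calling the pooled change disease progression when part of the sample is growing.

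**Masked decline is not what the documents expect.** Protocol section 1 describes the condition as not degenerative, with improvement in early childhood and then stability. A reader might infer that growth is hiding a real decline in this cohort; the documents do not support that. They support only that the planned test could not tell the two apart. Nor do they say why children's height is re-measured; that it is for growth is an inference.

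**Percent predicted is not a perfect correction.** If a patient at 70% of predicted distance P gained the full healthy increment g, the ratio (0.7P + g)/(P + g) would exceed 0.7 and drift upward. It is growth-neutral only under proportional scaling. The SAP also does not define predicted_distance_walked, and its demographics list names height at month 0 only. If baseline height was carried forward, the ratio would miss growth in height. For patients with contractures, height may itself be estimated from ulnar length. These points argue against replacing the pre-specified test, but not against a companion analysis.

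**The trial's conclusion is safe.** A reader might infer that the treatment comparison is compromised. It is not: success rests on isoprostane between arms, randomization balances children and adults, both arms grow, and the 6MWT model controls for baseline and then for age, sex and height. The SAP's closing allowance for further exploratory analyses leaves room for a size-adjusted look but does not specify one.

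**Conclusion.** The point holds as a gap in the natural-history analysis. The only planned 6MWT progression test cannot separate growth from disease in children, although the plan already holds a predicted distance for each visit and already uses percent predicted for vital capacity. Under the assumed ranges, the chance of a significant change without progression is about 5-28% at n=30 and 6-59% at n=76. The midpoint values of 8.5% and 14% are fairer single figures than the extremes, and all fall if patients gain only a fraction of the predicted rise. The true size depends on the share of children, their growth and the SD of change, none of which the documents give. This is an inexpensive improvement to Phase 1. It is not a threat to the randomized result.

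**What to change.** 1. Confirm what predicted_distance_walked is: metres or percent, which reference equation, and whether the month 6 value uses age and height updated to that visit. If it does not, recalculate it from the month 6 measurements.
2. In SAP natural-history item 2, keep the paired test of total distance in metres and also report it separately for patients under 18 and for adults.
3. Add a paired test of the month 0 to 6 change in percent-predicted distance (observed divided by predicted at the same visit), matching the treatment of FVC and SVC.
4. Base any statement about disease progression in children on the percent-predicted result, with the change in metres beside it.
5. Because the SAP (2 July 2018) postdates the data lock (29 March 2018), date the addition and label it supportive.

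Cost: one derived variable and one by-age table, with no new data collection if month 6 age and height are on file. The downsides are dependence on the reference equation, including its proportional-scaling assumption, and one more supportive analysis to report.

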A randomized, double-blinded, placebo controlled clinical trial of NAC in RYR1-RM patients will be performed to test the effect on oxidative stress, fatigability, and fatigue. The primary outcome measure will be 15-F2t-isoprostane for oxidative stress. Success will be defined as finding a significant difference in 15-F2t-isoprostane concentration between the treatment and placebo groups at the termination of the study. ***If successful, this study of NAC in RYR1-RM patients will provide the first treatment available for this debilitating muscle disease.***

2. Study objectives

Aim 1. To determine if NAC reduces oxidative stress in patients with RYR1-RM.

Hypothesis: Compared to the placebo group and baseline values for each patient, N-acetylcysteine will reduce oxidative stress in the treatment group as evidenced by: 1) decreased 15-F2t-isoprostane in urine, 2) decreased 2',7'-Dichlorodihydrofluorescein (DCFH) in biopsied muscle, and 3) increased glutathione (GSH) in blood. Exploratory markers of anaerobic threshold, fraction of inspired O₂, and tissue oxygenation by Near Infrared Spectroscopy (NIRS) will also be measured pre and post treatment.

Aim 2. To determine if NAC reduces fatigability and fatigue in patients with RYR1-RM.

Hypothesis: Compared to the placebo group and baseline values for each patient, N-acetylcysteine will reduce fatigability (objective construct) and fatigue (subjective construct) in the treatment group as evidenced by: (for fatigability) 1) the 6MWT, 2) timed function tests, 3) grip and pinch strength, as measured by Myotools 4) muscle fatigability by Biodex-; and (for fatigue) 5) Patient-Reported Outcomes Measurement Information System (PROMIS), 6) Functional Assessment Chronic Illness Therapy (FACIT) fatigue scale, 7) Fatigue scales: Multidimensional Fatigue Inventory (MFI).

As secondary and exploratory measures, we will also test the following pre and post treatment: CPET by cycle ergometry, Electrical Impedance Myography (EIM) to measure skeletal muscle health, muscle MRI to evaluate for subclinical muscle involvement as well as the health of muscle tissue, MFM for motor function, salivary fatigue biomarker index (FBI), melatonin, dehydroepiandrosterone (DHEA), the NeuroQoL scale, and qualitative interview for health related quality of life.

Aim 3. To determine values of study biomarkers, NIRS, muscle ultrasound, and MRI in age-matched healthy volunteers

3. Subjects:

a. Description of study populations

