In *RYR1*-RM myopathy patients, there will be no statistically significant difference in corrected 15-F2t-isoprostane concentration and/or corrected 15-F2t-Isop:PGF2 α ratio between NAC and placebo groups at month 12, after controlling for established *a priori* confounders.

Alternative Hypothesis (H₁)

At month 12, in *RYR1*-RM myopathy patients allocated to NAC treatment, there will be significantly decreased corrected 15-F2t-isoprostane concentration and/or 15-F2t-Isop:PGF2 α ratio compared to those allocated to placebo, after controlling for established *a priori* confounders.

2. Run a general linear model comparing month 12 6MWT total distance (min_6_distance_month12) between NAC and placebo groups controlling for baseline value. Run this model again controlling for established *a priori* confounders including age, sex, height. Variables that do not contribute significantly to the model may be removed.

Run this model again and control for one additional hypothetical confounder (post hoc): FVC % predicted.

Null Hypothesis (H₀)

In RYR1-RM myopathy patients, there will be no statistically significant difference in 6MWT total distance between NAC and placebo groups at month 12, after controlling for established *a priori* confounders.

Alternative Hypothesis (H₁)

At month 12, in RYR1-RM myopathy patients allocated to NAC treatment, there will be significantly increased 6MWT total distance compared to those allocated to placebo, after controlling for established *a priori* confounders.

Adverse Event Analysis

The 3 categories for AEs in the locked data are:

1. AE

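### SAP model 1 joins concentration and the PGF2α ratio by and/or, so a ratio outside the protocol's endpoint can meet the primary hypothesis alone, with more error than a single test

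*SAP*

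**What the plan says.** **SAP, Intervention phase analyses, model 1.** The general linear model is run on two month-12 variables: "corrected_f2-isop_month12, corrected_f2-isop_PGF2alpha_ratio_month12) between NAC and placebo groups controlling for pre-intervention value". It is then run again controlling for "confounders including age, sex, height, weight, BMI, smoking status, alcohol status", with the permission "Variables that do not contribute significantly to the model may be removed". All runs are made in both the per-protocol and the intent-to-treat (ITT) data.

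**SAP, hypotheses for model 1.** Both hypotheses join the two variables by and/or. The null is non-directional. The alternative counts only a decrease: "there will be significantly decreased corrected 15-F2t-isoprostane concentration and/or" the "ratio compared to those allocated to placebo, after controlling for established" confounders. No order of testing, hierarchy or division of alpha is stated.

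**SAP, Natural history phase analyses.** The SAP lists its own primary measures twice, both times without the ratio: "The mean values for the primary outcome measures (corrected 15-F2t-isoprostane concentration and 6MWT distance" in item 1, and "For the primary outcome measures (corrected 15-F2t-isoprostane concentration and 6MWT) change between 0 and 6-month time points will be assessed" in item 2.

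**Protocol.** The Summary in section 1 says "The primary outcome measure will be 15-F2t-isoprostane for oxidative stress". Section 10.a defines success as a significant reduction in urine 15-F2t-isoprostane on NAC against placebo. The outcome table in section 9 has no PGF2α ratio. Section 10.a names Student's t test for comparing the arms and, a few sentences later, general linear modeling to handle confounders. It sets alpha at 0.05. Section 10.b makes ITT the primary analysis.

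**The concern.** The SAP offers two ways to meet the hypothesis under its primary heading, and the protocol recognises only one. If the ratio is significant and concentration is not, the SAP hypothesis is met and the protocol's success rule is not. The same data then support opposite statements about the primary outcome. That conflict depends on no assumed correlation.

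The situation is a practical one. Section 10.b reports that the sample size recalculated from the trial's own isoprostane data was 182, against a planned 76, and that the study was closed to data analysis as a result. A non-significant concentration result is therefore a real possibility, and that is when a second route would matter.

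The model that decides is also open. The SAP hypotheses point to the confounder-adjusted model, but its covariates may be dropped by significance. The protocol names two analyses without ranking them.

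**Working it through.** **Inputs.** Alpha of 0.05 comes from protocol section 10.a. Two-sided testing comes from the sample-size text in section 10.b; neither document states the sidedness of the month-12 model. The two dependent variables come from SAP model 1. No correlation between them is given, so the values below are assumed.

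**The plan's own figure.** Section 10.b needs 38 per group for a glutathione change of 1.7 against 0, with SDs 2.34 and 2.80, two-sided 0.05 and 80% power.
- Sum of variances: 2.34² + 2.80² = 5.4756 + 7.84 = 13.3156.
- Normal approximation: 13.3156 × (1.960 + 0.842)² / 1.7² = 36.2, so 37 per group.
- Noncentral t with Satterthwaite degrees of freedom: power 0.798 at 37 and 0.809 at 38. The stated 38 reproduces.
- The interim boundary of 3.36 matches an O'Brien-Fleming-type boundary at two-sided 0.05 and 40% information (3.357).

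Both figures support two-sided 0.05 as the working level. Neither document states an error rate for the two-variable hypothesis.

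**Error of the and/or rule.** Let Z1 and Z2 be the two test statistics under the joint null, bivariate normal with correlation r, oriented so that a decrease is positive.
- Wrongly rejecting the null in either direction: 1 − P(|Z1| < 1.96, |Z2| < 1.96). At r = 0 this is 1 − 0.95² = 9.75%.
- Wrongly meeting the alternative, where only a decrease counts: 1 − P(Z1 < 1.96, Z2 < 1.96). At r = 0 this is 1 − 0.975² = 4.94%. At any r it is at most 2 × 2.5% = 5%.

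| Assumed r | Null rejected, either direction | Alternative met, decrease only |
|---|---|---|
| 0 | 9.75% | 4.94% |
| 0.5 | 9.07% | 4.54% |
| 0.8 | 7.81% | 3.90% |
| 0.9 | 7.04% | 3.52% |
| 0.95 | 6.46% | 3.23% |
| 0.99 | 5.66% | 2.83% |
| One test only | 5.00% | 2.50% |

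The two variables share the isoprostane measurement, so r = 0 is a limit and not an expectation.

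**Which analysis decides.** ITT is settled by protocol section 10.b. The covariate set is not: the SAP runs the model with the pre-intervention value only, then with seven further covariates, then possibly with some of them removed. The protocol adds a t test.

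**Cost of fixing the full covariate set.** If the seven extra covariates explain nothing, the variance of the arm difference is multiplied by 1 + p/(n − p − 3). Here p = 8 with the full set and p = 1 with the month-6 value alone.
- n = 76: (1 + 8/65) / (1 + 1/72) = 1.11.
- n = 50: (1 + 8/39) / (1 + 1/46) = 1.18.
- n = 40: (1 + 8/29) / (1 + 1/36) = 1.24.

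The target number of completers is 76; the documents do not give the number analysed.

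**The case against.** The strongest defence is that only the protocol defines success, and it does so on isoprostane alone. The SAP never calls the ratio primary, lists its primary measures twice without it, and uses and/or loosely in other hypotheses too. On this view the and/or is a drafting habit that one sentence would cure. Much of this stands: it limits the severity and means that the trial's success rule is not itself inflated. It does not remove the defect. The hypothesis under the primary heading still accepts the ratio alone, and nothing in the SAP says that the protocol's rule overrides it.

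Four stronger readings are tempting, and the documents do not support them.
- *The error always exceeds 5% at any correlation below 1.* This is so for rejecting the non-directional null by a difference in either direction. The alternative counts only a decrease, and at two-sided 0.05 its error stays at or below 5%.
- *The protocol's arm comparison is a t test, in plain conflict with the SAP.* Section 10.a also names general linear modeling for confounders. The gap is that it does not say which analysis decides.
- *Keeping both variables at 0.025 each would cut power from 80% to about 71%.* The 80% was calculated for glutathione. For isoprostane, section 10.b gives a required N of 182, so 80% is not the starting point.
- *The ratio was added with knowledge of results by arm.* The SAP of July 2018 does draw on files labelled as locked in March 2018. But the protocol says that only a statistician was unblinded, for the sample size recalculation, and that the investigators stay blinded until the study is complete.

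**Conclusion.** The point holds, as a should-fix. The and/or lets a variable outside the protocol's endpoint meet the SAP's primary-outcome hypothesis, and the two documents can disagree on the same data. Against a single test, the chance of a false rejection of the null rises from 5% to at most 9.75%, and the chance of falsely meeting the alternative from 2.5% to at most 5%. At the high correlations that a shared measurement makes plausible (0.8 to 0.9), the figures are 7.8% to 7.0% and 3.9% to 3.5%.

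These sizes rest on two-sided tests at 0.05, a joint null and assumed correlations. They do not count the 6MWT or the repeated model runs. The open covariate set is a further freedom and is not included in these figures.

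**What to change.** Before the investigators are unblinded:

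1. In the SAP, strike and/or and the ratio from both hypotheses of model 1.
2. Name one success test: corrected 15-F2t-isoprostane concentration at month 12, in the ITT set, from one general linear model. Fix its terms in advance as arm, month-6 value and the SAP's listed covariates, or a stated subset, with no removal by significance. A subset is reasonable, since BMI is computed from height and weight.
3. Label the ratio, the per-protocol set and any other covariate set as supportive.
4. In protocol section 10.a, state that this model, and not the t test, decides for this outcome.
5. As a minor clarification, say in the 6MWT model whether the baseline value means month 6, which the SAP elsewhere calls pre-intervention.

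With one test, the error returns to 5% two-sided, or 2.5% for a decrease. No new data or patients are needed. There are two costs. A significant ratio alone could no longer be presented as success. If the full covariate set is kept and explains nothing, the variance of the arm difference rises by about 11% at 76 patients, 18% at 50 and 24% at 40. A smaller fixed set would reduce that cost and hold the error equally well.
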